4.5 Analyses prior to end of scheduled follow-up visits

Any analyses conducted prior to the end of the scheduled follow-up visits should not compromise the integrity of the trial in terms of participant retention or safety or immunogenicity endpoint assessments. In particular, early unblinded analyses by treatment assignment require careful consideration and should be made available on a need to know basis only. .

4.5.1 Safety

During the course of the trial, unblinded analyses of safety data will be prepared approximately every 4 months during the study for review by the HVTN SMB. Ad hoc safety reports may also be prepared for SMB review at the request of the HVTN 120 PSRT. Refer to the process described in the HVTN unblinding MOP any requests for unblinded safety data prior to the end of the scheduled follow-up visits.

4.5.2 Immunogenicity

The unblinded analysis of the primary endpoint of CD4+ T-cell response rates measured at month 6.5 will be conducted when all participants have completed the visit and all samples have been analyzed. Unblinded results will not be made publicly available until participants have completed their month 12 visit. Unblinded data analyses of secondary and exploratory endpoints (ie, additional immunogenicity assays) measured at month 6.5 will occur after the unblinded CD4+ T-cell immunogenicity analysis since selection of secondary assays is dependent upon the primary analysis. Analysis of secondary and exploratory objectives for month 6.5 will take place after the primary analysis and may be performed when assay data are available for analysis from at least 80% of participants.

Analysis of anti-gp120 binding antibody response magnitudes measured at month 12 will be conducted when all participants have completed the visit and all samples have been analyzed. Unblinded analysis of secondary and exploratory endpoints from the month 12 timepoint will take place after the primary analysis of anti-gp120 binding antibody and may be performed when assay data are available for analysis from at least 80% of participants.

The Laboratory Program will review analysis reports prior to distribution to the protocol chairs, DAIDS, vaccine developer, and other key HVTN members and investigators. Distribution of reports will be limited to those with a need to know for the purpose of informing decisions related to future trials. The HVTN leadership must approve any other requests for HVTN immunogenicity analyses prior to the end of the scheduled follow-up visits.

5 SAFETY TABLES AND FIGURES

5.1 List of Tables (see mock tables in Appendix A)

SMB reports and Safety FSRs include the following tables.

- Enrollment Report
- Demographics and Study Product Administration Frequencies
- Overall Protocol Status
- Maximum Local Reactogenicity Summary
- Maximum Systemic Reactogenicity Summary
- Adverse Experiences by Body System and Severity – By Decreasing Frequency
- Adverse Experiences by Preferred Term and Severity – By Decreasing Frequency – Includes Severe, Potentially Life-threatening or Fatal Events Only
- Adverse Experiences by Preferred Term and Severity – By Decreasing Frequency – Includes Events of All Severities
- Adverse Experiences by Preferred Term and Relationship to Study Product – By Decreasing Frequency – Includes Related Events Only
- Adverse Experiences by Preferred Term and Relationship to Study Product – By Decreasing Frequency – Includes Events of Any Relationship
- Expedited Adverse Events (EAEs) Reported to the Regulatory Support Center (RSC)
- Pregnancy Listing
- Adverse Events of Special Interest

Safety FSRs include the following additional tables.

- Social Impact Summary
- Local Lab Value Summary Statistics
- Local Laboratory Values Meeting Grade 1 AE Criteria or Above

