1.2. Study Objectives and Endpoints

Primary objectives and endpoints

Primary objective 1

- To evaluate the safety and tolerability of ALVAC-HIV and bivalent gp120 protein/MF59 or bivalent gp120 protein/AS01_B.

Primary endpoints 1

- Severe local and systemic reactogenicity signs and symptoms (pain, tenderness, erythema, induration, fever, malaise/fatigue, myalgia, headache, nausea, vomiting, chills, arthralgia) up to 7 days after each vaccine dose
- AEs by body system, Medical Dictionary for Regulatory Activities (MedDRA) preferred term, severity, and assessed relationship to study products up to 30 days after each vaccine dose
- SAEs, AESIs, and new chronic conditions (requiring medical intervention for ≥ 30 days) throughout the study
- Laboratory measures: white blood cells (WBC), neutrophils, lymphocytes, hemoglobin, platelets, alanine aminotransferase (ALT), aspartate aminotransferase (AST), alkaline phosphate (ALP), and creatinine at baseline and following vaccinations
- AEs leading to early participant withdrawal or early discontinuation of study products administration throughout the study.

Primary objective 2

- To compare HIV-specific CD4+ T-cell response rates at the month 6.5 timepoint (2 weeks after the fourth vaccination) of ALVAC-HIV and bivalent gp120 protein/MF59 to each of the bivalent gp120 protein/AS01_B vaccine regimens.

Primary endpoint 2

- HIV-specific CD4+ T-cell response rates as assessed by flow cytometry.

Primary objective 3

- To compare HIV-specific Env-gp120 binding antibody response magnitudes at the month 12 timepoint (6 months after the fourth vaccination) of ALVAC-HIV and bivalent gp120 protein/MF59 to each of the bivalent gp120 protein/AS01_B vaccine regimens.

Primary endpoint 3

- HIV-specific Env-gp120 binding antibody response magnitude as assessed by multiplex assay.

Secondary objectives and endpoints

Secondary objective 1

- To further evaluate the systemic immune responses and the durability of immunogenicity of each vaccine regimen at the month 6.5 and month 12 timepoints.

Secondary endpoint 1

- HIV-specific total IgG binding antibody response breadth and magnitude as assessed by multiplex assay.
- Anti –V1/V2 scaffold IgG binding antibody responses as assessed by multiplex assay.
- HIV-specific CD4+ and CD8+ T-cell responses as assessed by flow cytometry.
- Additional immunogenicity assays may be performed on blood samples based on the HVTN Laboratory Assay Algorithm

Exploratory objectives

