1.4. Blinding

Participants and site staff (except for site pharmacists) will be blinded as to participants' treatment group assignments. Study product assignments are accessible to those HVTN CRS

pharmacists, DAIDS protocol pharmacists and contract monitors, and SDMC staff who are required to know this information in order to ensure proper trial conduct. Any discussion of study product assignment between pharmacy staff and any other HVTN CRS staff is prohibited. The HVTN SMB members also are unblinded to treatment assignment in order to conduct review of trial safety.

When a participant leaves the trial prior to study completion, the participant will be told he or she must wait until all participants are unblinded to learn his or her treatment assignment.

In some cases, the CRS, PSRT, or study sponsor may believe unblinding of the site PI and participant would be appropriate to facilitate the clinical management of an AE or SAE. The HVTN Unblinding MOP specifies procedures for emergency unblinding, and for early unblinding for medical reasons.

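### Both by-arm laboratory tables go to the final safety report only, so the SMB is assured no tabular view of a primary safety endpoint while dosing continues

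*SAP*

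**What the plan says.** Section 1.2 includes among the endpoints for primary objective 1 "Laboratory measures: white blood cells (WBC), neutrophils, lymphocytes, hemoglobin, platelets" and four further analytes, nine in all, at baseline and after vaccination.

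Section 1.4 gives the SMB its role: "The HVTN SMB members also are unblinded to treatment assignment in order to conduct review of trial safety". Section 4.5.1 sets the rhythm: "unblinded analyses of safety data will be prepared approximately every 4 months during the study for review by the HVTN SMB". It also allows ad hoc SMB reports when the PSRT asks for them.

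Section 4.3.3 specifies the laboratory outputs by treatment group: boxplots by visit; summary statistics by timepoint, with change from baseline; and the number and percentage of participants at Grade 1 or above at each postvaccination timepoint. It adds that reportable abnormalities without a clinical diagnosis are counted in the AE tables.

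Section 5.1 then assigns tables to reports. One list opens "SMB reports and Safety FSRs include the following tables". A second opens "Safety FSRs include the following additional tables", and it holds "Local Lab Value Summary Statistics" and "Local Laboratory Values Meeting Grade 1 AE Criteria or Above". Section 5.2 gives the SMB's participant listings. Section 5.3 lists graphs, including laboratory boxplots for the nine analytes, without naming a report.

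**The concern.** The SAP makes laboratory measures a primary safety endpoint and makes the SMB the unblinded reviewer of safety, yet allocates the by-arm laboratory tables to a report written when the study is over. Site staff other than pharmacists are blinded, so they cannot compare arms. The AE tables carry only abnormalities that were reportable, and under section 4.3.2 each participant is counted once per category at maximum severity, so timing and change from baseline are lost.

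At stake is how early an arm-level laboratory difference could be seen. The three vaccine arms differ in adjuvant and protein dose, and the protein is given only at months 3 and 6. A difference in low-grade values or in change from baseline, appearing after those doses in one arm, is what the two tables are built to show. As allocated, the SMB has no assurance of seeing it in tabular form before dosing ends.

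**Working it through.** There is no figure in the SAP to reproduce. The check has two parts: which outputs reach the SMB, and how many of its reports fall during dosing.

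**Outputs by report (sections 5.1 to 5.3)**

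| Output list | Items | Giving laboratory safety values |
|---|---|---|
| 5.1, shared by SMB reports and Safety FSRs | 13 | 0 |
| 5.1, Safety FSRs only | 3 | 2 |
| 5.2, SMB participant listings | 9 | 0 (the one item naming laboratory results concerns HIV infection status) |
| 5.3, graphs | 3 | 1 (boxplots; report not stated) |

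**What each route would show the SMB (sections 4.3.2, 4.3.3 and 4.5.1)**

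- *AE tables:* by treatment group, but only reportable abnormalities, once per participant per category, with no timepoint and no change from baseline.
- *Listing of severe, life-threatening or fatal AEs:* individual severe abnormalities reported as AEs; nothing at lower grades.
- *Boxplots:* by group and visit, with quartiles, outliers and, if appropriate, lines at the abnormal boundaries. They would show a shift in the distribution, but not counts of participants at Grade 1 or above. Delivery to the SMB is not stated.
- *Ad hoc reports:* possible, but only on a PSRT request.
- *The two laboratory tables:* counts at Grade 1 or above and change from baseline, by group and timepoint. Assigned to the FSR only.

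**Timing**

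Inputs from section 1.1: total duration 18 months including enrolment and follow-up; 12 months of visits per participant; vaccinations at months 0, 1, 3 and 6; 50 + 50 + 50 + 10 = 160 participants.

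- Enrolment, by subtraction: 18 − 12 = about 6 months. This is an inference; the SAP does not state it.
- Last fourth dose: 6 + 6 = about study month 12.
- Reporting intervals over the whole study: 18 / 4 = 4.5, so about 4 reports.
- Counting from study month 4, reports fall near months 4, 8, 12 and 16. Two come clearly before the last dose and a third at about that time.
- Section 1 says SMB reporting starts shortly after enrolment opens. If the first report came at month 1, the series would be 1, 5, 9, 13 and so on; from month 2 it would be 2, 6, 10, 14 and so on. Each gives three reports before month 12.

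So two or three SMB reports fall during dosing, and none of them is assigned a laboratory table. The first report to which those tables are assigned is the Safety FSR, after all 160 participants have passed their last scheduled dose.

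**The case against.** The strongest reply is that nothing here is contradictory. Section 5.1 makes an explicit two-tier split, and no section promises the SMB a table for every primary endpoint. That is correct: this is a weakness in a stated allocation, not an error.

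The second reply is that the boxplots largely meet the need. They are by group and visit, cover all nine analytes, and a shift in a distribution is what they display. Sections 5.1 and 5.2 name their reports while 5.3 carries no restriction, and its other two graphs show reactogenicity maxima, whose tables go to both reports. Reading 5.3 as covering SMB reports is therefore at least as natural as excluding them. This stands in large part: if the boxplots are supplied, the remaining gap is the graded counts and the change-from-baseline summaries. But the SAP leaves delivery unstated.

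Third, reportable abnormalities reach the SMB by arm through AE tables covering all severities. The SAP gives no reporting threshold, so if low-grade abnormalities are reportable, those tables already carry part of what the Grade 1 or above table would add. The size of the gap is unknown for that reason.

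A reader might infer that the SMB sees no arm-level laboratory data, or that only the SMB could ever recognise a difference between arms. The SAP supports neither. The routes above exist, and section 1.4 also gives access to assignments to data-centre (SDMC) staff who need them. Nor does the SAP say what laboratory data the PSRT sees or whether it is blinded.

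**Conclusion.** The point holds in a limited form. Section 5.1 reserves both by-arm laboratory tables for the Safety FSR and no listing in 5.2 fills the gap, although laboratory measures are a primary safety endpoint and the SMB is the unblinded reviewer. The SMB is thus assured no by-arm, by-timepoint counts at Grade 1 or above and no change-from-baseline summaries in the two or three reports issued during dosing.

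It would be tempting to count all of the roughly four reports over 18 months, but those after about month 12 fall outside the dosing period and do not bear on this harm.

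Severity is modest. The conclusion rests on about 6 months of enrolment and a regular 4-month cycle. The Appendix A mock tables and the protocol are not at hand, so any laboratory output for the SMB specified there could not be checked. Nothing here suggests that a signal was missed.

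**What to change.** In section 5.1, move the two laboratory tables into the list shared by SMB reports and Safety FSRs. If length is a concern, move at least the Grade 1 or above table. In section 5.3, state that the laboratory boxplots are part of each SMB report. If the present split is deliberate, give the reason in 5.1.

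The change is to SAP wording, and section 4.3.3 already specifies these outputs by treatment group, so no new analysis has to be defined. The cost is a longer SMB report and earlier cleaning of laboratory data. The SAP does not say whether the tables have been programmed, so some programming may also have to be brought forward.

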5.2 Participant Listings

The following listings of participant-level data are included in the SMB reports.

- Discontinuations
- Pregnancies
- Severe or Life-Threatening Local and Systemic Reactogenicities
- Moderate or Severe Erythema and Induration
- Expedited Adverse Experiences (EAEs)
- Adverse Experiences of Special Interest (AESIs)
- Severe, Life-Threatening, or Fatal Adverse Experiences
- Study Product Administration Errors

- HIV Infection Results from Lab and Reported by Site

5.3 List of Graphs

- Maximum Local Reactogenicities
- Maximum Systemic Reactogenicities
- Boxplots of laboratory values for white blood cells (WBC), neutrophils, lymphocytes, hemoglobin, platelets, alanine aminotransferase (ALT), aspartate aminotransferase (AST), alkaline phosphate (ALP), and creatinine at baseline and following vaccinations

6 IMMUNOGENICITY TABLES AND FIGURES, BY ASSAY

6.1 Intracellular Cytokine Staining

Flow cytometry will be used to examine vaccine specific CD4+ and CD8+ T cell responses following stimulation of PBMCs with synthetic HIV peptides that span the proteins encoded by the vaccine. Vaccine specific T-cell response magnitudes and response rates will be assessed at the Month 6.5 timepoint/Visit 10 (2 weeks after the fourth vaccination) and the Month 12 timepoint/Visit 12 (6 months after the fourth vaccination). Visit 10 analyses will be conducted first. Afterwards Visit 12 analyses will be conducted and combined with the Visit 10 analyses, once Visit 12 specimens become available. Contingent on the results of the Visit 10 and Visit 12 analyses, additional reports may be generated for Visit 7. The following peptide pools will be used:

Peptide Pool	Pool ID	Lot Number
LAI-Gag	PP500025	11S227
LAI gp41 TM	PP502556	15H008AB
Env-1-ZM96	PP502442	14C093A
Env-2-ZM96	PP502446	14C097A
TV1 gp120	PP502557	15H020A
1086 gp120	PP502551	15H015A

The following functional markers will be measured from a 17-colormetric panel: AViD, CCR7, CD14, CD56, CD45RA, CXCR5, ICOS (CD278), PD-1 (CD279), CD3, CD4, CD8, CD154, IFN- γ , Granzyme B, IL-2, IL-4, IL-17a, and TNF α . The initial reports will present IL-2 and IFN- γ responses. Subsequent reports may be produced to include data from the other functional markers.

All analyses are performed on LAI-Gag, LAI-Gag gp41 TM, Env-1-ZM96, Env-2-ZM96, TV1 gp120 Env, and 1086 gp120 Env, individually and according to 2 levels of pooling:

1. Env-ZM96: Sum of Env-1-ZM96 and Env-2-ZM96
2. Any Env: the maximum of Env ZM96, 1086 gp120, and TV1 gp120, where Env ZM96 is the sum of Env-1-ZM96 and Env-2-ZM96; 3

3. Any HIV: the sum of Any Env, LAI-Gag gp 41 TM and LAI-Gag.

Positivity calls and subsequent analyses are performed separately for CD4+ and CD8+ T cell responses. Fisher's exact test criteria will be used for positivity calls before assays on all samples are complete. After, MIMOSA criteria will be used for positivity calls. If at least one peptide pool for a specific HIV-1 gene is positive, then the overall response to the gene is considered positive. If any peptide pool is positive, then the overall response to HIV-1 (Any HIV) for that T-cell subset is considered positive.

Positive response rates are compared between treatment groups using Barnard's exact test. Response magnitudes are compared between treatment groups using Wilcoxon rank sum test. Positive response rates are compared within treatment group, across timepoints using McNemar's test. Response magnitudes are compared within treatment group, across timepoints using the Wilcoxon signed rank test. Statistical tests with an unadjusted p-value ≤ 0.05 will be considered statistically significant.

The following comparisons of the immune response rate and magnitude will be performed:

- Pairwise comparisons of response rates and response magnitudes between all treatment groups.
- Pairwise comparisons of response rates and response magnitudes within treatment group, between the Visit 10 and Visit 12 timepoints.
- If additional assays are performed at Visit 7, then between time point comparisons, within treatment group, will be performed between Visit 7 and Visit 10 and between Visit 7 and Visit 12.

6.1.1 List of Tables

- Response rate table by lab, T cell subset, peptide pool, visit, day, and group/treatment arm for cells expressing either IL-2 and/or IFN- γ using Fisher's exact test criteria and/or MIMOSA criteria.
- Summary statistics (i.e., min, mean, median, max) of response magnitudes among responders for T-cell subset, peptide pool, visit, and group/treatment arm.
- Summary statistics (i.e., min, mean, median, max) of response magnitudes among all participants (positive and negative responders) for T-cell subset, peptide pool, visit, and group/treatment arm.
- Response rate and/or response magnitude comparisons of treatment arms as specified above.
- Response rate and/or response magnitude comparisons across time points as specified above.
- Listing of positive responders for cells expressing either IL-2 and/or IFN- γ based on the criteria used for the response rate table.

6.1.2 List of Graphs

- Boxplots of background-adjusted IFN- γ and/or IL-2 response magnitude by T cell subset, peptide pool, visit, and group/treatment arm using Fisher exact test and/or MIMOSA criteria. Graphs will be displayed with treatment groups side by side with one peptide pool, one T-cell subset and one visit per graph. Above the boxplots, concordant barplots of the response rates will be shown.
- Boxplots of background-adjusted IFN- γ and/or IL-2 response magnitude by T cell subset, HIV protein, visit, and group/treatment arm using Fisher exact test and/or MIMOSA criteria. Graphs will be displayed with treatment groups and visits side by side with one peptide pool, one T-cell subset per graph. Spaghetti plots that connect each participant response across visits will be superimposed on the boxplots. Above the boxplots, concordant barplots of the response rates will be shown.

6.2 Neutralizing Antibody

This section will be completed upon receipt of the lab study plan for the NAb assay.

6.3 Binding Antibody Multiplex Assay

Serum HIV-1-specific IgG antibody binding responses were measured at a 1:50 dilution against all antigens in the following table. Serum samples were tested at a starting 1:50 dilution followed by a 2-fold serial dilution for a total of six dilution points for antigens 00MSA 4076 gp140, 1086C_D7gp120.avi/293F, 96ZM651.D11gp120.avi, A1.con.env03 140 CF, Con 6 gp120/B, Con S gp140 CFI, and TV1c8_D11gp120.avi/293F at month 6.5. Serum IgG responses against specified antigens were measured on a Bio-Plex instrument (Bio-Rad) using a standardized custom HIV-1 Luminex assay (Tomaras et al. 2008; Tomaras et al. 2013; Haynes et al. 2012; Yates et al. 2014; Yates et al. 2018; Zolla-Pazner et al. 2014). The readout was background-subtracted mean fluorescence intensity (MFI), where background referred to a plate level control (i.e., a blank well run on each plate). Standard positive and negative controls were included in each assay to ensure specificity and for maintaining consistency and reproducibility between assays. The positive control includes purified polyclonal IgG from HIV subjects (HIVIG) using a 10-point standard curve (4PL fit) and CH58 V1V2 IgG (Liao et al. 2013). The negative controls were NHS (HIV-1 sero-negative human sera) and blank beads.

Several criteria were used to determine if data from an assay were acceptable and could be statistically analyzed. First, the blood draw date must have been within the allowable visit window as determined by the protocol. Post-infection samples from HIV-infected participants are excluded. Second, if the blank bead negative control exceeded 5,000 MFI, the sample was repeated. If the repeat value exceeded 5,000 MFI, the sample was excluded from analysis due to high background. The preset assay criteria for sample reporting were: coefficient of variation (CV) per duplicate values for each sample are < 20% and ≥ 50 beads counted per sample. To control for protein performance, the preset criteria include that the positive control titration in each assay must be within ± 3 standard deviations of the mean for each antigen. The AUTC is calculated using the trapezoidal rule based on the raw MFI values truncated at zero across the log base 10 dilution per participant, isotype, antigen, and visit.

Binding Antibody Multiplex Assay (BAMA) testing will be performed on serum samples from each participant in the protocol at visit 2 (month 0, baseline), visit 10 (month 6.5, 2 weeks post the 4th vaccination), and visit 12 (month 12, 6 months post the 4th vaccination). Specimens from other timepoints as well as other HIV antigens and antibody isotypes may be assayed based on the results of the initial assay. If sufficient immunogenicity is observed for the primary analysis antigens, additional assays will be performed using the exploratory antigens.

The following table lists the antigens for the analysis.

Panel	Antigen	Clade	Endpoint
Vaccine gp120 panel	1086C_D7gp120.avi/293F	C	Primary objective 3
	96ZM651.D11gp120.avi	C	Primary objective 3
	TV1c8_D11gp120.avi/293F	C	Primary objective 3
Vaccine V1V2 panel	C.1086C_V1_V2 Tags	C	Secondary objective 1
	gp70-96ZM651.02 V1v2	C	Secondary objective 1
	gp70-TV1.21 V1V2	C	Secondary objective 1
	gp70-TV1.GSKvacV1V2/293F	C	Secondary objective 1
Other V1V2	gp70_B.CaseA_V1_V2	B	Exploratory objective
	gp70_B.CaseA2_V1/V2/169K	B	Exploratory objective
Conensus gp140/gp120	Con 6 gp120/B	M	Exploratory objective
	Con S gp140 CFI	M	Exploratory objective
Other gp140	00MSA 4076 gp140	A	Exploratory objective
	A1.con.env03 140 CF	A	Exploratory objective
gp41	gp41	B	Exploratory objective

MFI will be employed for this essay. The frequency of positive responders (% responders) will be tabulated to access HIV binding antibody responses between placebo and vaccine groups from MFI readouts.

Samples from post-enrollment visits are declared to have a positive response if they meet three conditions:

1. The Net MFI (MFI*, i.e., MFI minus Blank values, where 'Blank value' refers to a plate-specific background measure) were \geq antigen-specific cutoff (based on the 95th percentile of the baseline samples).
2. The MFI* values were greater than 3 times the baseline MFI*.
3. The MFI values are greater than 3 times the baseline MFI values.

